11. DATA SAFETY MONITORING PLAN

A committee consisting of two physicians, [name] (Assistant Professor, Division of Infectious Diseases) and [name] MD, (Assistant Professor, Division of Pulmonary and Critical Care) has been created. [name] and [name] have agreed to be part of the committee and will not have any direct participation or interests in the study. The committee will meet emergently in the event of the reported SAE and consider the future course based on the outcome of the event. If no SAE is reported, the committee will meet every 6 months to assess the safety and review the AEs.

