All activities outlined in **Table 1** would be billed to the sponsor to compensate [name] for her time and effort to support our participants and overall project goals and needs. The donor related activities will take place before the research participant is seen for informed consent during the screening visit (see **Table 2**). This is done to ensure that the donor has been screened for infectious diseases in a timely manner and that [name] has ample time to prepare the allogenic human fecal specimen in her lab for the transplant on the enrollment visit. Donors will be screened every four weeks which is standard protocol for [name] lab. More details about the donor screening process and requirements are listed in the protocol section **3.6 a) Donor Stool Collection and Processing**.

Table 1. Donor Related Study Activities

Donor Activity	Specific Test Ordered	Visit
Blood/Serology Testing	
 1. Hepatitis A IgM and IgG 2. Hepatitis B S Ab/Sag/Core Ab 3. Hepatitis C Ab 4. RPR 5. Human Immunodeficiency Virus (HIV) 1 and 2 Antibody 	Donor Screening (every four weeks)
Stool Testing	
 1. Clostridium Difficile PCR 2. Salmonella, Shigella, and Campylobacter 3. Ova and parasites 4. H. Pylori antigen 5. 5.Vancomycin resistant Enterococcus (VRE) 6. Carbapenemase resistant Enterobacteriaceae 	
Fecal Sample Preparation for Donation ¹	N/A	

¹The fecal sample will be prepared for the FMT in [name] laboratory on site. Please refer to section 3.6 a for more detailed information regarding the donor fecal sample processing activities.

Table 2 outlines a total of five complete research visits for each research participant: screening (initial), enrollment (transplant), 2 weeks post-transplant (may be a phone call at the discretion of the physician), 4 weeks post-transplant, and 3 months post-transplant. For the initial or screening visit, research participants will first complete the informed consent process with a member of the research team. Upon completion of the informed consent process, the participant will receive phlebotomy to collect blood for plasma chemistries, CBC with differential, and platelet counts.

Urine will also be collected and screened for basic urinalysis. Women of child bearing potential

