Timeline: All the proposed aims and enrollments will be carried out within 24-month period. We do anticipate a large proportion of eligible subjects may travel to Emory as the interest in this therapeutic platform is quite high with us already receiving numerous requests.

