6. REQUIRED NUMBER OF PARTICIPANTS

A total of 11 patients with IPAA/UC related pouchitis will be enrolled over 12 months as part of this pilot study.

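### Routine committee review of non-serious adverse events follows the calendar only, so on the 12-month enrollment plan about half of the 11 subjects are treated before the first review

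*Combined protocol and SAP*

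**What the plan says.** Section 11 sets up a committee of two physicians who "will not have any direct participation or interests in the study". It has two triggers for meeting. The first is a serious event: "The committee will meet emergently in the event of the reported SAE and consider the future course based on the outcome of the event". The second is the calendar: "If no SAE is reported, the committee will meet every 6 months to assess the safety and review the AEs". The section does not say when the six months begin.

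Section 6 gives the size and pace of the study: "A total of 11 patients with IPAA/UC related pouchitis will be enrolled over 12 months as part of this pilot study". The timeline paragraph in section 3.6 b gives a longer period: "All the proposed aims and enrollments will be carried out within 24-month period". It adds that "interest in this therapeutic platform is quite high with us already receiving numerous requests", but states no accrual rate. Table 2 places the single transplant at the enrollment visit, so a subject who completes that visit has been treated.

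Section 12.4 requires outside reporting, including to the DSMB, only for events that are both serious and unexpected. Section 12.1 grades an event as Severe when it prevents work or ordinary activities; section 12.3 does not list that as a criterion for seriousness. Section 9 mentions a Simon two-stage design, but only for deciding on future enrollment.

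**The concern.** Safety and tolerability is the primary objective in section 3.1. Independent review of early subjects can help later ones only if it takes place while later subjects are still untreated. Under a calendar rule, the number treated before the first routine review depends on how fast subjects arrive, and the protocol does not control that.

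The documents contain no review after a set number of subjects, no spacing between subjects and no committee trigger below an SAE. Several non-serious reactions, even ones graded Severe, could therefore build up across recipients of standard-donor material before anyone outside the study team looks at the pattern. The information would exist early: the clinical part of the activity index, which includes fever and rectal bleeding, is scored at week 2.

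**Working it through.** The protocol gives no figure for the number treated before the first review and no power calculation behind the 11, so there is nothing to reproduce. The check is on timing.

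**Inputs.** N = 11 (section 6). Review interval = 6 months (section 11). Accrual period T = 12 months (section 6) or, on another reading, 24 months (section 3.6 timeline). Enrolled equals treated (Table 2).

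**Assumptions.** Accrual is even, and the 6-month clock starts at first enrollment. The documents state neither.

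**Formula.** Treated by the first routine review = 11 × min(1, 6/T).

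| T (months) | Calculation | Treated | Share |
|---|---|---|---|
| 6 or less | 11 × 1 | 11 | 100% |
| 9 | 11 × 6/9 | 7.33 | 67% |
| 12 | 11 × 6/12 | 5.5 | 50% |
| 18 | 11 × 6/18 | 3.67 | 33% |
| 24 | 11 × 6/24 | 2.75 | 25% |

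At T = 12 this means 5 or 6 subjects, and all 11 are treated by the second review at month 12. If entry times are random rather than even, the number treated by month 6 is Binomial(11, 0.5), with a 95% range of 2 to 9.

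**Follow-up available at month 6.** Twelve weeks is 12/(52/12) = 2.77 months. At T = 12, 11 × (6 − 2.77)/12 = 2.96, so about 3 subjects would have completed follow-up.

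**Would there be anything to review earlier?** The documents give no rate for non-serious events, so these risks are assumptions. The chance of at least one event among n subjects is 1 − (1 − p)^n.

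| Assumed risk p | n = 3 | n = 5 | n = 6 |
|---|---|---|---|
| 10% | 27% | 41% | 47% |
| 20% | 49% | 67% | 74% |
| 30% | 66% | 83% | 88% |

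**Gain from a look after three subjects.** At p = 30% and T = 12, expected events before the first review fall from 5.5 × 0.3 = 1.65 to 3 × 0.3 = 0.9, a difference of 0.75. At p = 20% the difference is 2.5 × 0.2 = 0.5. At T = 24 it is essentially nil, because only 2.75 subjects precede the month-6 review anyway. At T = 6 the calendar rule gives 11 × 0.3 = 3.3 expected events.

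**Fit with the planned pace.** At T = 12 a subject arrives every 12/11 = 1.09 months, about 33 days. The week 2 visit window closes on day 14 + 3 = 17. That leaves about 16 days for a meeting before the next subject is expected.

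**The case against.** The strongest reply is that this is a stated design choice for a small, single-administration pilot. The committee is independent, any reported SAE brings an urgent meeting, and investigators see each subject at 2 weeks, 4 weeks and 3 months. Section 12.3 is also broad. It covers medically significant events and those needing intervention to prevent a listed outcome, and it leaves room for the investigator's judgment. That stands, and it confines the point to events the investigator judges non-serious. A reader might infer that fever, bleeding or worsening pouchitis could never prompt an early meeting. The documents do not support that, because serious forms of each would.

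A reader might also infer that all 11 subjects will probably be treated before any review. That needs accrual at least twice as fast as section 6 plans. The timeline paragraph reports interest and requests, not eligible subjects or a rate. Its 24-month period points the other way, although it covers all aims as well as enrollment and may be only an outer limit. If the clock starts before first enrollment, fewer subjects precede the first review.

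Finally, the counts 3 and 6 are not derived from any criterion, and the week 2 contact may be a telephone call without biological samples. Both remarks are fair. The counts are examples, and an early look would rest mainly on reported symptoms. Neither remark removes the dependence of the present rule on accrual speed.

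**Conclusion.** The point holds for non-serious adverse events. With even accrual and a clock starting at first enrollment, about half of the subjects (5.5 of 11) are treated before the first routine independent review on the 12-month period, the only one the protocol gives for enrollment alone. The share is about a quarter (2.75) if 24 months is the accrual period, and all 11 only if accrual takes 6 months or less.

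It would go too far to conclude that the review comes too late to change anything. On the 12-month plan about half of the subjects are still untreated at month 6. Nor do the documents show that any subject would be harmed by the present schedule; the expected difference at planned accrual is less than one non-serious event under the assumed 30% risk.

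This is a cheap improvement rather than a flaw that invalidates the study. Confidence is medium, because the size depends on an accrual period the protocol gives in two ways and on a clock start it does not give.

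**What to change.** Amend section 11 in three respects.

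- Have the existing two-member committee review cumulative adverse events after early numbers of treated subjects, for example when the 3rd and the 6th have completed the week 2 contact, and in any case at least every 6 months.
- State the event that starts the 6-month clock.
- Reconcile the 12-month enrollment period in section 6 with the 24-month period in the section 3.6 timeline.

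Whether treatment should pause for a review, and any stopping criterion, is for the sponsor and the committee to decide; none is proposed here. Without a pause, a further subject could be treated before a review takes place if accrual is fast.

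The cost is two short meetings of an existing committee and a few lines of protocol text. No new staff, visits or procedures are needed.

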12. CLINICAL ADVERSE EVENTS

FMT in UC-associated Pouchitis

Version 3.0, date finalized 06/26/2017

An adverse event is any untoward medical occurrence in a subject administered the study procedure and which does not necessarily have a causal relationship with the study procedure. An adverse event can thus be any unfavorable and unintended sign, symptom, or disease temporally associated with the use of the study drug, whether or not considered related to the study drug. Pre-existing conditions that worsen during the study are considered adverse events. For the purposes of this study, AE's related to study procedures will be collected.

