3. STUDY DESIGN

The primary investigative design will be a single arm study to determine if FMT has the potential to be used in the treatment of chronic pouchitis.

3.1 *Study Objectives:*

Primary Objective: To determine the safety and tolerability of fecal microbiota transplant (FMT) in treatment of chronic pouchitis

Secondary Objective: To study the microbial environment of IPAA/UC associated pouches in patients presenting with symptoms of pouchitis with and without endoscopy-visualized pouchitis and to assess the impact of the therapy on the patient's perceived quality of life

3.2 *Study design Type/Phase:* This is a two center, Phase 1 open label study designed to determine the safety, tolerability and use of fecal transplant in patients with pouchitis and to study the differences in microbiome in patients before and after treatment with FMT.

3.3 *Sites Centers of Research:* This study will be conducted in the Emory Clinic- Adult Digestive Disease Clinic and Colorectal Surgery Clinic, the Emory Center Endoscopy Center, and St. Joseph's Hospital (SJH) in Atlanta, GA.

3.4 *Measures to minimize/avoid bias:* Eligible subjects will be given options of other treatments if they choose not to participate.

3.5 *Study duration:* The total duration of the study for each patient will be twelve weeks.

3.6 *Study Procedures*

The following protocol essentially requires two sets of study procedures. One set of study procedures outlines testing requirements for the donor of allogenic human feces (see **Table 1.** Donor Related Study Activities). The other set outlines activities and expectations of the research participant who will receive the donated stool specimen (see **Table 2.** Research Participant Study Activities). The donor set of activities will be managed by [name], a sub-investigator and Associate Professor of Medicine within the Division of Infectious Diseases. In the past, [name] has overseen the donor recruitment and screening within previous FMT trials via ordering the appropriate antibody screens, fecal sample preparation (e.g. use of saline, etc.) and any other necessary tests to ensure that the fecal specimen is non-infectious and safe for insertion into research participants. [name] still oversees this process and prepares the allogenic human fecal FMT in UC-associated Pouchitis

Version 3.0, date finalized 06/26/2017

donation in her lab on site. However, she will not be able to provide these activities listed in **Table 1** for effort.

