9. DATA ANALYSIS

Patients will be identified by physicians on this protocol in The Emory Clinic or Emory

FMT in UC-associated Pouchitis

Version 3.0, date finalized 06/26/2017

University Hospital. Patients will be consented using an IRB approved informed consent and undergo the procedure on their follow up visit.

Since this is a pilot study, no formal power calculation is provided. Descriptive statistics and ANOVA will be used to detect differences between groups. One-sample t-test or Wilcoxon's signed rank-tests will be used to see if there were any significant changes in PDAI and QOL scores before and after transplant. A Simon's two stage design will be used to decide whether to enroll more patients in the future.

Data relating to laboratory results will be obtained through the EMR computerized patient information systems EML microbiological reports. A dataset will be created in a secure file, with access given only to authorized study staff.

A list of possible cases that have been reviewed for inclusion will be secured by study staff. This list will contain subject name, birth date, medical record number, and the number of the corresponding data abstraction sheet. Such a list will be maintained so as not to duplicate the abstraction of a single subject. Once the data from all included subjects is entered into a database, the list of identifiable patient information will be destroyed.

Data analysis will be performed with Microsoft Excel, SAS Institute software, and SPSS software.

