10. ENDPOINTS

The primary endpoint of this study will be resolution of clinical pouchitis symptoms using the clinical component of the modified pouchitis disease activity index without relapse for 3 months. Secondary endpoints include 16S ribosomal gene sequencing and metabolomic profiles that are more favorable (as defined by the donor microbiota). An additional secondary endpoint will be improvement of quality of life as determined by QOL questionnaires.

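### Safety and tolerability are the primary objective, but no endpoint or named summary measures them, and adverse event collection is narrowed to procedure-related events

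*Combined protocol and SAP*

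**What the plan says.** Section 3.1 gives the aim as "Primary Objective: To determine the safety and tolerability of fecal microbiota transplant (FMT) in treatment of chronic pouchitis". Section 3.2 describes a "Phase 1 open label study designed to determine the safety, tolerability and use of fecal transplant in patients with pouchitis".

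Section 10 states: "The primary endpoint of this study will be resolution of clinical pouchitis symptoms using the clinical component of the modified pouchitis disease activity index", sustained for 3 months. It continues: "Secondary endpoints include 16S ribosomal gene sequencing and metabolomic profiles that are more favorable", and adds quality of life as a further secondary endpoint.

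Section 9 says: "Descriptive statistics and ANOVA will be used to detect differences between groups". It then names one-sample t-tests or Wilcoxon signed-rank tests for "any significant changes in PDAI and QOL scores before and after transplant".

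Section 12 defines an AE as an unfavourable occurrence in time with the treatment, "whether or not considered related to the study drug", and counts worsening of pre-existing conditions. It ends: "For the purposes of this study, AE's related to study procedures will be collected".

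Section 12.2 has the investigator grade each AE's relationship to FMT as Probable, Possible, Remote or Unrelated. Section 11 sets up a committee that reviews AEs every 6 months and meets urgently if a serious event is reported.

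**The concern.** Two problems meet here.

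First, the stated primary question has nothing to be reported against. A reader of the final report could not tell which safety result was planned as the answer.

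Second, the data that would answer it pass through a causality filter before they are recorded. The study has no control arm and no blinding, so attribution of an infection or flare some weeks after FMT is a judgement made by someone who knows the treatment. Section 7 names transmitted infection and immune stimulation as the main FMT risks, and either could have a plausible alternative explanation. An event that was never logged cannot be regraded later, and the committee in Section 11 would be working from the same log.

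**Working it through.** The plan has no safety figure to reproduce. Section 6 gives 11 patients, and Section 9 says that no power calculation was made. No safety rate, threshold or precision target is stated. The check is therefore a comparison of sections, plus one argument about direction.

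**1. Objective against endpoints and analysis.**

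| Section | Content | Safety measure? |
|---|---|---|
| 3.1 | Primary objective: safety and tolerability | This is the question |
| 10, primary | Clinical mPDAI symptom resolution | No |
| 10, secondary | 16S sequencing, metabolomic profiles, quality of life | No |
| 9, named tests | PDAI and quality-of-life change | No |
| 9, general sentence | Descriptive statistics and ANOVA for group differences | Could cover an AE listing; AEs not mentioned |

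Sections 11, 12.1 and 12.2 supply a committee, severity grades and relationship grades. The ingredients of a safety summary exist, but the summary is not named. Section 1 adds a further version of the aims: its first aim is the utility of FMT, which fits the Section 10 endpoint and not the Section 3.1 objective.

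**2. The collection sentence against its neighbours.**

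- The Section 12 definition is broad and the closing sentence takes a subset of it.
- Section 12.2 provides Remote and Unrelated grades. The Unrelated grade is for events put down wholly to outside causes, with disease and environment as examples. Such events would mostly not enter a log restricted to procedure-related AEs.
- Section 12.2 grades relationship to FMT, whereas the collection sentence refers to study procedures. Section 12.2 also does not say whether Possible counts as related. A well-timed flare that the underlying disease might also explain meets the first two Possible criteria, and whether it must be collected is not stated.
- Section 3.6 b watches for AEs of any kind, but only for 30 minutes after FMT.
- Table 2 has no AE row. Nothing in the text that could be read says that all AEs are collected through week 12. Some pages were removed from that text and could not be checked.

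**3. Direction of the effect on the any-AE proportion.** Let S be the subjects with at least one AE under the Section 12 definition, and R the subjects with at least one AE that passes the filter. Every recorded AE is an AE, so R is contained in S and |R|/11 ≤ |S|/11. The two are equal when every subject with an AE has at least one that is recorded. The documents give no AE rate and no share judged related, so the gap cannot be computed. For events actually caused by FMT the direction is open, because attribution can err either way.

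**4. What would still be seen.** Table 2 schedules the clinical mPDAI, a physical exam and a CBC at every visit with no causality condition. Worsening pouchitis would show in the scores, though not necessarily as an AE. This backstop is partial. The clinical component covers stool frequency, bleeding, urgency or cramps, and fever. The 2-week visit may be by telephone, in which case no biological samples are collected except possibly a mailed stool sample.

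**The case against.** The best defence is that a protocol may define AEs broadly and choose to collect fewer. The collection sentence opens by limiting itself to this study, so it is a decision on scope. That stands: a reader might infer that Section 12 contradicts itself, and the text does not support that.

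A reader might also infer that the Remote and Unrelated grades could never be used. They could: a bleed from a biopsy is procedure-related yet may be unrelated to FMT, and the examples under Unrelated are not exhaustive. The fit is poor, but it is not a proven conflict.

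A third inference is that Section 12.4 conflicts with the sentence, because it reports serious and unexpected events without mentioning relatedness. Section 12.3 weakens this. It describes a serious event as one that suggests a hazard or side effect, which can be read as already implying a link to the intervention. The point does not rely on Section 12.4.

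Finally, pilot status explains the missing power calculation, and the general reference to descriptive statistics may be meant to include AEs. Neither supplies an endpoint for the primary objective.

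**Conclusion.** The point holds. The primary objective has no matching endpoint and no named summary. The collection sentence, if followed as written, makes an unblinded attribution the condition for recording non-serious AEs. The first part rests on Sections 3.1, 9 and 10 alone and is enough to require a change. The second assumes that the sentence is applied literally. It lacks the word only, so the two centres could read it differently.

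The size is not known. A reader might infer that the AE rate will be understated by some definite amount, but the documents support only that the recorded any-AE proportion is at or below the true one, with a shortfall that may be zero. Nor do they support the view that worsening disease would go unseen, given the scheduled scores, exams and blood counts.

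**What to change.** 1. Replace the closing sentence of Section 12. Collect all AEs and serious AEs regardless of relationship, from the first study procedure after consent to the 3-month visit. The window should not start at FMT: screening phlebotomy, pouch preparation (enemas and loperamide), sedation, sigmoidoscopy and biopsy all come before it, and the current sentence covers events from those procedures. Record relationship to FMT (Section 12.2 grades) and relationship to other study procedures as separate variables. Ask about AEs at each scheduled contact, including a telephone visit, and add an AE row to Table 2.

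2. Add a safety endpoint to Sections 9 and 10: the number and proportion of subjects with any AE, any FMT-related AE, any procedure-related AE and any serious AE, with exact 95% confidence intervals. State which Section 12.2 grades count as related.

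3. Reconcile Sections 1, 3.1 and 10 on what is primary, so that the primary objective has a matching primary or co-primary endpoint.

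The cost is protocol wording and a longer AE log in 11 subjects, with no extra visits. The reported AE rate may look higher because it will include events of the underlying disease. The intervals will be wide: no events in 11 subjects gives an exact two-sided 95% interval from 0 to 1 − 0.025^(1/11) = 28.5%. That describes what the summary can deliver at this sample size and is not evidence on the size of any bias.
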